**LIST OF ABBREVIATIONS AND RELEVANT DEFINITIONS**

ABR	General Assessment and Registration form (ABR form), the application form that is required for submission to the accredited Ethics Committee; in Dutch: Algemeen Beoordelings- en Registratieformulier (ABR-formulier)
AE	Adverse Event
AR	Adverse Reaction
CA	Competent Authority
CCMO	Central Committee on Research Involving Human Subjects; in Dutch: Centrale Commissie Mensgebonden Onderzoek
CV	Curriculum Vitae
DSMB	Data Safety Monitoring Board
ERABS	Enhanced Recovery After Bariatric Surgery
EU	European Union
EudraCT	European drug regulatory affairs Clinical Trials
GCP	Good Clinical Practice
IB	Investigator's Brochure
IC	Informed Consent
IMP	Investigational Medicinal Product
IMPD	Investigational Medicinal Product Dossier
METC	Medical research ethics committee (MREC); in Dutch: medisch-ethische toetsingscommissie (METC)
LRYGB	Laparoscopic Roux-en-Y Gastric Bypass
LSG	Laparoscopic Sleeve Gastrectomy
(S)AE	(Serious) Adverse Event
Sponsor	The sponsor is the party that commissions the organisation or performance of the research, for example a pharmaceutical company, academic hospital, scientific organisation or investigator. A party that provides funding for a study but does not commission it is not regarded as the sponsor, but referred to as a subsidising party.
SUSAR	Suspected Unexpected Serious Adverse Reaction
TA	Tranexamic acid
WMO	Medical Research Involving Human Subjects Act; in Dutch: Wet Medisch-wetenschappelijk Onderzoek met Mensen

## SUMMARY

**Rationale:** Fast-track protocols are frequently used in bariatric surgery and often include short-term thromboprophylaxis and short length of hospital stay. These treatment strategies may negatively affect the occurrence and diagnosis of postoperative hemorrhage. Over the years, the rates of venous thromboembolic events (VTE) decrease, while there seems to be an increase in the occurrence of postoperative hemorrhage. Tranexamic acid (TA) is a plasminogen inhibitor which inhibits fibrinolysis. Peroperative administration of TA may lower the incidence of postoperative hemorrhage.

**Objective:** This trial aims to investigate if peroperative administration of TA can reduce the peroperative and postoperative hemorrhage rates in laparoscopic sleeve gastrectomy.

**Study design:** This is a double-blind, single center randomized controlled trial.

**Study population:** Patients eligible for bariatric surgery according to the IFSO guidelines and undergoing a laparoscopic sleeve gastrectomy. Patients unwilling to give informed consent, patients with a medical history of bleeding or VTE and patients that use therapeutic anticoagulants will be excluded.

**Intervention (if applicable):** Patients are randomized between 2 groups: 1) Single dose of 1500 mg TA to be administered during induction of the procedure by anesthesiologist, and 2) Standard protocol with administration of placebo infusion.

**Main study parameters/endpoints:** Primary outcome measure is peroperative use of hemostatic clips. Secondary outcome measures are the decrease in hemoglobin after the procedure, rates of postoperative hemorrhage (i.e. hemorrhage needing administration of packed cells or a surgical or radiological re-intervention) and rates of VTE.

**Nature and extent of the burden and risks associated with participation, benefit and group relatedness:** All patients will be required to undergo one additional blood drawing in the week prior to the procedure which will be performed at their weighing appointment, meaning that this will not require an extra hospital visit. TA has very little side effects. Therefore we conclude that the expected benefits of the intervention outweigh the minor risks involved.

## 1. INTRODUCTION AND RATIONALE

Because of the increasing rates of morbid obesity and herewith increasing requests for bariatric surgery, the popularity of fast-track protocols is increasing. These Enhanced Recovery After Bariatric Surgery (ERABS) protocols often include short-term thromboprophylaxis and short length of hospital stay (LOS), with the aim to discharge patients on the first postoperative day(1, 2). Even though ERABS has many positive outcomes, it may also negatively affect the diagnosis of postoperative hemorrhage due to the short time window for diagnosing postoperative complications.

Most current literature states that postoperative hemorrhage occurs in 2.0% of patients undergoing laparoscopic sleeve gastrectomy (LSG) and in 1.5-3.1% of patients undergoing a laparoscopic Roux-en-Y gastric bypass (LRYGB)(3, 4). It is described that over the years, there seems to be an increase in the occurrence of postoperative hemorrhage, while the risk of venous thromboembolic events (VTE) is decreasing(5). In our center, overall postoperative hemorrhage rates of LRYGB and LSG have been stable since 2014, with more hemorrhage occurring after a LSG (2.2%) than after a LRYGB (1.3%). The rates of peroperative hemorrhage requiring hemostatic clips was 63.3% between January 2017 and March 2019. The rate of diagnosed VTE within 3 months postoperative is 0.05% since 2014 in this center.

Tranexamic acid (TA) is a plasminogen inhibitor that can be used to inhibit fibrinolysis during or after surgery and thus minimize the risk of developing perioperative hemorrhage. Little is known about the use of TA in bariatric surgery. Nevertheless, in several other surgical areas such as for coronary-artery surgery and arthroplasty, perioperative administration of TA has proven its value in preventing postoperative hemorrhage (6-8). Until now, the use of TA to prevent postoperative hemorrhage in bariatric surgery is once described by Hussain et al.(9). The authors performed a meta-analysis of administration of TA during laparoscopic sleeve gastrectomies and concluded that administration of TA is a simple yet effective way to lower the rates of staple line hemorrhage, while shortening the length of surgery. In the end of 2018, Klaassen et al described that reoperations may be prevented due to postoperative administration of TA in case of a suspicion of an already present hemorrhage(10).

Because of the serious risks of postoperative hemorrhage, the need for preventive measures in bariatric fast-track surgery is increasing. This trial aims to investigate if peroperative administration of TA can reduce the postoperative hemorrhage rates in laparoscopic sleeve gastrectomy.

## 2. OBJECTIVES

Primary Objective: Does the peroperative administration of TA lead to lesser use of peroperative extra hemostatic clips?

Secondary Objective(s): Does the peroperative administration of TA lead to a smaller hemoglobin decrease 1 day postoperatively and a lower reoperation rate within 30 days postoperative due to hemorrhage, or an increase in venous thromboembolic events within 3 months postoperative?

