### **3. STUDY DESIGN**

This is a double-blind, single center randomized placebo-controlled trial that will last for approximately 1 year, depending on the speed of inclusion. We aim to include 100 patients.

Patients are equally randomized between 2 groups: 1) Single dose of TA to be administered during induction of the procedure by anesthesiologist, and 2) Standard protocol with administration of a placebo (sodium chloride).

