#### **4.4 Sample size calculation**

The performed power analysis (power= 80%, alfa=5% two-sided) calculated a required sample size of  $2 \times 36 = 72$  patients. The analysis was based on an expected 50% decrease of the percentage of patients for whom placement of hemostatic staples was required peroperatively.

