### **8.3 Study procedures**

An extra blood sample (1 EDTA tube) is obtained in the week preoperative by venipuncture. From this blood sample, hemoglobin tests are performed in the hospital's laboratory. Postoperative hemoglobin value will be obtained from the blood sample that is performed in all bariatric patients on the first postoperative day. Information on peroperative use of hemostatic staples, administration of packed cells, postoperative tranexamic acid, rates of postoperative hemorrhage and VTE are obtained from the electronic patient file. Routine venous duplex ultrasound will not be performed. Therefore, only clinically significant VTEs are registered.

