### **10.2 Secondary study parameter(s)**

Differences in rates of DVT (yes/no), PE (yes/no) and in rates of administration of postoperative tranexamic acid (yes/no) between the 2 groups will be calculated using Chi-Square (Fisher's Exact) tests.

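### The secondary question whether TA increases VTE cannot be answered by the planned separate DVT and PE tests; any-VTE counts with exact confidence limits would fit the declared endpoint

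*Protocol*

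**What the plan says.** - **Objective (Protocol, section 2).** The secondary objective is put as a question. Its last part asks about "or an increase in venous thromboembolic events within 3 months postoperative".
- **Endpoint (section 8.1.2).** The declared secondary outcome is the rate of VTE within 3 months, as one endpoint.
- **Analysis (section 10.2).** The planned comparison is of "Differences in rates of DVT (yes/no), PE (yes/no") and of postoperative TA use, by Chi-Square or Fisher's exact test. No test or estimate of any VTE is named. The two-sided 5% threshold is given in section 10.1.
- **Background rate (section 1).** "The rate of diagnosed VTE within 3 months postoperative is 0.05% since 2014 in this center". It is not stated to be specific to sleeve gastrectomy.
- **Ascertainment (section 8.3).** There is no routine duplex scan. "Therefore, only clinically significant VTEs are registered".
- **Size (section 3).** "We aim to include 100 patients", and "Patients are equally randomized between 2 groups", which gives 50 per arm.
- **Power (section 4.4).** The only calculation ("power= 80%, alfa=5% two-sided") is for the primary outcome. No power is stated for VTE.

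**The concern.** The protocol sets a yes/no question about harm and also fixes the method that is to answer it. By the protocol's own background rate, that method has next to no chance of answering yes for any increase one could reasonably expect. The named tests also do not match the endpoint: VTE is declared, DVT and PE are tested, and a patient with a VTE at another site would appear in neither comparison.

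What is at stake is how a secondary safety result can be reported. A p-value above 0.05 will almost surely be obtained and says almost nothing. A count with exact limits shows the reader how large an increase the data leave open.

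**Working it through.** **1. The plan's own figure.** Section 4.4 assumes an "expected 50% decrease of the percentage of patients for whom placement of hemostatic staples was required peroperatively". With the 63.3% in section 1 this is 63.3% v 31.65%. The unpooled normal formula gives

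n = (1.960 + 0.842)² × (0.633×0.367 + 0.3165×0.6835) / 0.3165² = 7.849 × 0.4486 / 0.1002 = 35.15, so 36 per arm, 72 in all.

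The stated figure is reproduced. It concerns staples only.

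**2. Expected VTEs.** At 0.05%:
- 100 patients: 100 × 0.0005 = 0.05 events, and P(no VTE in the trial) = 0.9995¹⁰⁰ = 95.1%.
- 72 patients: 72 × 0.0005 = 0.036 events, and 0.9995⁷² = 96.5%.

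If TA changes the rate in its own arm of 50, P(no VTE in either arm) is
- doubling to 0.1%: 0.9995⁵⁰ × 0.999⁵⁰ = 92.8%;
- ten-fold, to 0.5%: 0.9995⁵⁰ × 0.995⁵⁰ = 75.9%.

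**3. Smallest significant result.** With x events v 0 and 50 per arm, the two-sided Fisher p is 2 × C(50,x)/C(100,x):
- 5 v 0: p = 0.056;
- 6 v 0: p = 0.027.

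Six of 50 is 12%, and 0.12/0.0005 = 240 times the centre's rate. With 36 per arm, 6 v 0 is again needed (5 v 0 gives 0.054, 6 v 0 gives 0.025). An uncorrected Chi-Square would reach p = 0.041 at 4 v 0, but the expected count is then only 2 events per arm, where Fisher is the appropriate choice. Even 4/50 = 8% is 160 times the background.

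**4. Power of Fisher's test.** The protocol names no increase to detect, so a range is assumed (control 0.05%, 50 per arm, exact enumeration):

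| TA-arm risk | Multiple of 0.05% | Power |
|---|---|---|
| 0.1% | 2 | about 1.5 × 10⁻¹¹ |
| 0.5% | 10 | about 2 × 10⁻⁷ |
| 2.5% | 50 | 0.15% |
| 5% | 100 | 3.7% |
| 10% | 200 | 37.7% |
| 15.5% | about 310 | 80% |

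The 5% row can be checked by hand. P(at least 6 of 50 at 5%) = 0.0378, and P(0 of 50 at 0.05%) = 0.9753. Their product is 0.0368, and results with a control event add the rest. With 36 per arm the power in that row is 0.8%.

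**5. The protocol's own risk figure.** Section 6.4 lists thromboembolic events with TA at 0.01–0.1%. Adding the top of that range to the background gives 0.15%. Power is then about 2 × 10⁻¹⁰, and P(no VTE in either arm) = 0.9995⁵⁰ × 0.9985⁵⁰ = 90.5%.

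**6. What a zero count leaves open.** The exact two-sided 95% upper limit for 0 of n is 1 − 0.025^(1/n): 7.1% for n = 50 and 9.7% for n = 36. The former is about 142 times 0.05%.

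**7. Scale.** For 80% power at two-sided 5% (pooled formula, no continuity correction), a doubling from 0.05% needs about 47,057 patients per arm and a ten-fold rise about 2,125. A larger trial is therefore not the remedy.

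**The case against.** The strongest reply is that nothing stated is wrong. VTE is secondary, no power is claimed for it, no decision rule hangs on the test, and section 12.6 calls the study a pilot. Recording and comparing a rare harm in a small trial is normal practice. This stands: low power alone would not be a finding, and it is why the point is minor.

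A second reply is that interval methods and cautions on interpretation are usually left to the SAP, which is not at hand. That holds in part. But the protocol has itself chosen the question, the endpoint and the tests, and these do not fit one another.

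Two stronger readings are tempting, and the documents do not support them.
- A reader might infer that a null test will be reported as proof of safety. No section says so. Section 13.2 calls TA proven safe on prior knowledge, to justify skipping part of the risk analysis. It does not rest on this trial's VTE result. The risk of such a reading is an inference.
- A reader might infer that a null result is certain whatever TA does. It is not: power reaches 80% at a TA-arm risk of about 15.5%. The statement holds only for credible effects.

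Nor should the dalteparin prophylaxis or the restriction to clinical events be counted as lowering the rate further. Both are probably already reflected in the centre's rate of diagnosed VTE. Splitting VTE into DVT and PE costs little power, since there is almost none to lose, and section 8.3 records VTE without limiting it to those two sites. The split is a mismatch with the endpoint rather than a loss of data.

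**Conclusion.** The point holds in a limited form. Section 2 poses a question on VTE that the tests in section 10.2 cannot answer, and those tests omit the endpoint declared in section 8.1.2. With 50 per arm and a 0.05% control rate, about 0.05 events are expected, 6 v 0 is needed for significance, and power is 3.7% for a 100-fold rise.

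This rests on the centre-wide 0.05% applying to sleeve patients, on 1:1 allocation of 100 patients, and on an assumed range of effects. The conclusion is not sensitive to these: the TA-arm risk would have to be some hundreds of times the background before the test became useful. Severity is minor, and the change is a cheap improvement.

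**What to change.** - **Section 2:** word the VTE part of the secondary objective as describing VTE within 3 months in each arm.
- **Section 10.2:** replace the separate DVT and PE tests with the number of patients with any VTE per arm, with exact 95% confidence limits for each arm and for the difference. DVT and PE may be listed descriptively.
- **Section 10.2:** state that a zero count or a non-significant difference does not exclude a relevant increase, and give the scale: 0 of 50 leaves an upper limit of 7.1%.

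The cost is wording only. No data, visits or patients are added, and the primary analysis and sample size are untouched. The trial gives up a VTE hypothesis test that it could not support.

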### **3. STUDY DESIGN**

This is a double-blind, single center randomized placebo-controlled trial that will last for approximately 1 year, depending on the speed of inclusion. We aim to include 100 patients.

Patients are equally randomized between 2 groups: 1) Single dose of TA to be administered during induction of the procedure by anesthesiologist, and 2) Standard protocol with administration of a placebo (sodium chloride).

### **4. STUDY POPULATION**

#### **4.1 Population (base)**

All patients found suitable for bariatric surgery according to the international guidelines and undergoing a laparoscopic sleeve gastrectomy (LSG) will be asked to participate in the study. All patients will follow the hospital's Enhanced Recovery After Bariatric Surgery (ERABS) protocol, which includes chemical thromboprophylaxis (Dalteparine 1 dd 5000 IE during hospital admission).

#### **4.2 Inclusion criteria**

In order to be eligible to participate in this study, a subject must meet all of the following criteria: Primary bariatric procedure; good command of the Dutch or English language.

#### **4.3 Exclusion criteria**

A potential subject who meets any of the following criteria will be excluded from participation in this study: Patients unwilling to give informed consent, patients with a medical history of bleeding or VTE and patients who use therapeutic anticoagulants. Patients will also be excluded in case of peroperative arterial bleeding or (iatrogenic) bleeding coming from surrounding organs or vascular structures such as the liver or the spleen.

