### **8.2 Randomisation, blinding and treatment allocation**

After obtaining informed consent at the outpatient clinic of the surgical or anesthesiological department, patients will be randomized into 1 of the 2 groups using Variable Block Randomization software by Ciwit B.V. (Castor EDC). Patients will either receive tranexamic acid or placebo (sodium chloride) during induction. Patient, surgical team and anesthesiological team will be blinded for the treatment, as the hospital pharmacy will prepare the infusion bags for each individual patient.

Availability of the patient's individualized infusion bag will be checked at the Time Out Procedure (TOP). The coordinating researcher is unblinded in order to be able to consult the treatment arm in case of emergency.

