### **8.4 Withdrawal of individual subjects**

Subjects can leave the study at any time for any reason if they wish to do so without any consequences. The investigator can decide to withdraw a subject from the study for urgent medical reasons, for example such as mentioned in the exclusion criteria.

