### **8.5 Replacement of individual subjects after withdrawal**

After withdrawal, individual subjects will be replaced by including new patients at the outpatient clinic to guarantee the needed number for sufficient power for analysis.

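### Section 4.3 excludes patients for bleeding seen during surgery, after randomisation and dosing, so the analysed set is selected on an event close to the primary endpoint

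*Protocol*

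**What the plan says.** The relevant steps stand in separate sections of the protocol.

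- **Randomisation (8.2)** follows consent at the outpatient clinic, before surgery.
- **Dosing (5.1, 8.2)** is at induction: "Patients will either receive tranexamic acid or placebo (sodium chloride) during induction".
- **Exclusion (4.3)**: "Patients will also be excluded in case of peroperative arterial bleeding or (iatrogenic) bleeding coming from surrounding organs or vascular structures", with the liver and the spleen as examples.
- **Withdrawal (8.4)**: "The investigator can decide to withdraw a subject from the study for urgent medical reasons, for example such as mentioned in the exclusion criteria".
- **Replacement (8.5)**: after withdrawal, "individual subjects will be replaced by including new patients at the outpatient clinic to guarantee the needed number for sufficient power for analysis".
- **Primary endpoint (8.1.1, 10.1)** is use of haemostatic staples (clips in the summary and section 2), yes or no, compared by chi-square test. Section 10 names no set of patients for this test.
- **Blinding (8.2)** covers the patient, the surgical team and the anaesthesia team. The coordinating researcher is unblinded, for emergencies.
- **Follow-up (8.6, 9.2.2)**: patients withdrawn from treatment are followed under the bariatric guidelines, and serious adverse events are reported for three months after surgery.

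**The concern.** The 4.3 sentence is listed as an eligibility criterion but works as removal after randomisation, because no one can know before the operation whether it applies. Its trigger is intra-operative bleeding. The endpoint is clip use during the same operation, which section 1 itself describes as peroperative haemorrhage requiring clips, and the study drug is given to reduce perioperative haemorrhage.

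Randomisation makes the arms comparable as allocated. If the drug alters how often the excluded bleeds occur, the patients left in each arm are no longer comparable, and enrolling new patients restores the number but not the comparability. If the drug does not alter them, the restricted set still estimates a different effect from the one in all operated patients. The haemoglobin, postoperative haemorrhage and VTE comparisons are exposed to the same selection.

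**Working it through.** **1. The plan's own sample size.** Inputs: "power= 80%, alfa=5% two-sided" and an "expected 50% decrease of the percentage of patients for whom placement of hemostatic staples was required peroperatively" (4.4); "Patients are equally randomized between 2 groups" (section 3). Section 4.4 does not restate the control rate, so it is taken from section 1: "The rates of peroperative hemorrhage requiring hemostatic clips was 63.3% between January 2017 and March 2019". Half of 63.3% is 31.65%. With unpooled variance:

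n = [p1(1−p1) + p2(1−p2)] × (1.96 + 0.8416)² / (p1−p2)²
= (0.2323 + 0.2163) × 7.849 / 0.3165² = 35.15

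Rounded up, this is 36 per arm or 72 in total, as the protocol states. The sample size is not in dispute, and it supports 63.3% and 31.65% as the planning rates.

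**2. Effect of exclusion on the estimate.** The protocol gives no rate for the excluded bleeds. *Assumptions:* a share e of an arm is excluded, and every excluded patient had clips. Then

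analysed rate = (p − e) / (1 − e)

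With true rates of 63.3% and 31.65% (difference 31.7 points, risk ratio 0.50):

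| Excluded, control / tranexamic acid | Control | Tranexamic acid | Difference (points) | Risk ratio |
|---|---|---|---|---|
| none | 63.3% | 31.65% | 31.7 | 0.50 |
| 2% / 2% | 62.6% | 30.3% | 32.3 | 0.48 |
| 10% / 10% | 59.2% | 24.1% | 35.2 | 0.41 |
| 10% / 2% | 59.2% | 30.3% | 29.0 | 0.51 |

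For example, in the third row, (0.633 − 0.10)/0.90 = 0.592, (0.3165 − 0.10)/0.90 = 0.241, and 0.241/0.592 = 0.41. Equal exclusion enlarges the apparent effect here. Heavier exclusion in the control arm, which would follow if the drug prevents such bleeds, shrinks it slightly.

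**3. Effect on the test when there is no true difference.** Take 63.3% clip use in both arms and 50 analysed per arm. With analysed rates a and b and d = a − b, the rejection probability is

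Φ[(d − 1.96·se0)/se1] + Φ[(−d − 1.96·se0)/se1]

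where se0 = √[2p̄(1−p̄)/n], p̄ is the mean of a and b, and se1 = √{[a(1−a) + b(1−b)]/n}.

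- Equal exclusion: a = b, so type I error stays at 5.0%.
- 10% against 5%: 59.2% and 61.4%, about 5.6%.
- 10% against 0%: 59.2% and 63.3%. Here se0 = 0.0974, se1 = 0.0973 and d = −0.041, giving 0.0086 + 0.0615, or about 7.0%.

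**4. Whether replacement is needed.** Section 3 plans 100 patients against 72 required, a margin of 28. With a pooled-variance test at 50 per arm, se0 = 0.0999 and se1 = 0.0947, so power = Φ[(0.3165 − 1.96 × 0.0999)/0.0947] = Φ(1.27), or 89.9%.

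**The case against.** The best defence is that the surgical and anaesthesia teams are blinded, and that the sentence is probably meant to set aside surgical injury that an antifibrinolytic would not be expected to prevent. If so, exclusion should be balanced, and balanced exclusion leaves type I error at 5%. This stands as a limit on the size of the problem and against any suggestion of deliberate imbalance. It does not remove the problem. Blinding cannot protect the comparison if the drug changes the frequency of these bleeds, and even equal exclusion changes the estimated effect in the table.

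A separate SAP might define an all-randomised set. It would then conflict with 4.3, which takes these patients out of the study.

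Four stronger readings are tempting, and the protocol does not support them.

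- *Arterial staple-line bleeders are certainly removed.* The phrase about surrounding organs and vessels may also qualify the arterial bleeding. The wording is ambiguous, and that is as far as it goes.
- *The rule favours tranexamic acid.* The table shows that the bias can run either way.
- *Every such patient is replaced.* Section 8.4 says the investigator can decide to withdraw and cites the exclusion criteria only as an example. The path to replacement is open but not automatic.
- *Dosed patients vanish from safety follow-up.* Sections 8.6 and 9.2.2 continue follow-up and serious adverse event reporting. What is missing is any statement that puts these patients back into the between-arm comparisons.

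**Conclusion.** The point holds and should be corrected before the analysis. As written, sections 4.3, 8.4 and 8.5 allow the analysed set to be chosen by an intra-operative bleeding event that occurs after randomisation and dosing, sits close to the primary endpoint and may be affected by treatment. Following the plan can therefore give a biased primary result.

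Neither size nor direction can be settled from the protocol. Under the stated assumptions (2% to 10% excluded per arm, all of them clip users), a true risk ratio of 0.50 would appear as anything from 0.41 to 0.51, and type I error would reach about 7% if 10% were excluded from one arm and none from the other. If these bleeds are rare and unrelated to treatment, the effect is small.

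**What to change.** - **4.3 and 8.4:** remove intra-operative bleeding as a ground for exclusion from the study or the analysis, including the reference to it in 8.4.
- **Section 10:** analyse all randomised patients who undergo the operation in their allocated arm, for the primary and secondary endpoints. Call this modified intention to treat, and report by arm those randomised but not operated on.
- **Bleeds:** record arterial and adjacent-organ bleeding by arm, with a definition that settles whether staple-line arterial bleeding counts. Run the analysis without these patients as a sensitivity analysis only.
- **8.5:** replace no patient who has been operated on. This also avoids both analysing and replacing a patient who was operated on but not dosed. Replacement is not needed for power.

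The cost is protocol wording. No extra patients or procedures are needed, since section 8.3 already takes clip use and the clinical outcomes from the patient file and the postoperative haemoglobin from routine sampling. The small downside is that clip use unrelated to the staple line adds some noise to the primary analysis; the sensitivity analysis will show how much it matters.
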